12.2.2 Power Calculations for Continuous Variables in the Case Control Study

Formulas for the calculation of study size and power for continuous variables have been developed by Walter (Walter, 1980) and by Lubin, Gail and Ershow (Lubin et al, 1988). Here, the derivations of Lubin et al. will be used to evaluate the operating characteristics of this study. The general sample size formula used in this evaluation is:

$$N \stackrel{!}{=} \frac{(\hat{e}\%1)}{\hat{e}} \frac{[Z_{a} \acute{o}_{x} \% Z_{a} \{(\hat{e}\acute{o}_{1}^{2}\%\acute{o}_{o}^{2})/(\hat{e}\%1)\}^{1/2}]^{2}}{(\mu_{1}\&\mu_{o})^{2}}$$

where

$$\acute{o}_{\div}^2 \ ' \ (\acute{o}_1^2 \, \% \, \acute{e} \acute{o}_0^2) / (\acute{e} \% 1) \, \% (\mu_1 \, \& \mu_0)^2 \acute{e} / (\acute{e} \% 1)^2$$

and

$$\mu_{i}' \left\{ mxf(x)P(D' i^{*}x)dx \right\} \left\{ mf(x)P(D' i^{*}x)dx \right\}^{\&1}$$
$$\delta_{i}^{2'} \left\{ mx^{2}f(x)P(D' i^{*}x)dx \right\} \left\{ mf(x)P(D' i^{*}x)dx \right\}^{\&1} \&\mu_{i}^{2}$$

In the above formula, μ_1 and \dot{o}_1^2 are the mean variance of the case exposure variable and μ_0 and \dot{o}_0^2 are the mean and variance of the control exposure variable. The proposed number of cases and controls is large enough to detect small effects (either in terms of linear risk or in terms of exponential risk). As such, the above formula can be simplified to:

N'
$$\frac{(\hat{e}\%1)(Z_{\dot{a}}\%Z_{\hat{a}})^2 \acute{o}^2}{\hat{e}(\mu_1 \& \mu_0)^2}$$

This simplification occurs because as the effect size gets small, $\dot{o}_{\pm}^2 \cdot \dot{o}_{1}^2 \cdot \dot{o}_{0}^2 \cdot \dot{o}^2$. This formula can be rearranged to determine the effect size $(\mu_1 \& \mu_0)/\dot{o}$ that can be detected with specified alpha level, power, and number of case control pairs. With the proposed of 720 cases and 720 controls, there will be better than 90% power to detect effect sizes of at least 0.16 standard deviations, a small effect size.

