12.2.3 Subgroup Analyses

As part of ACCESS, Clinical Center investigators may want to make comparisons of cases and controls within certain strata. For instance, there could be comparisons of female cases and controls, comparisons of black cases and controls, and comparisons of erythema nodosum cases with their matched controls. Each of these subgroup comparisons will bring with it a different number of cases and controls and power for making comparisons. Effect sizes that could be detected in one subgroup analysis, might not be detected in another analysis. Power analyses have been performed for statistical comparisons that will be performed in subgroups representing 7%, 14%, 25%, 50% and 75% of the entire case control study population. These percentages may be representative of comparisons for a small substudy (7% and 14%), within a sarcoidosis category (20%), within a gender comparison (50%), and within the black population (75%, published reports put the percentage of sarcoidosis cases who are black between 60% and 80% in some cities). Power calculations for binary exposure variables when performing analyses in subgroups are presented in Tables 3 through 12. There is a substantial change in the odds ratios that can be detected with adequate power depending upon the number of cases in the subgroup. For instance, fixing the odds ratio at 0.7, the correlation between case-control response at 0.5, and the proportion of controls exposed at 0.3, there is 54.8%, 83.7% and 95.0% power to detect this odds ratio for 180, 360 and 540 case control pairs, respectively.

As part of each subgroup analysis, a statistical test will be performed to determine if the findings relating to exposures in one subgroup correspond to the findings in the complimentary subgroup (an interaction test). For instance if a risk factor is discovered for females, is that risk

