factor also present and at the same level of magnitude in males or is it different. For binary exposure variables a matched case control regression model will be used with terms for the subgroup, the exposure, and the exposure-subgroup interaction in the model. For a case control design with one case and one control, the Cox Proportional Hazards model can be used by creating a dummy variable that always lists the case and "failing" first with control "censored" after the case "failure time". Power calculations for the factorial term in the Cox Model have been published (Peterson and George, 1993). In general the statistical efficiency of the interaction test is lower than the main effects test. For instance, with 50% of the population in one subgroup and 50% in the complimentary subgroup, the efficiency of the interaction test is one half that of the main effects test.

As an example, the current study design has at least 80% percent power to detect an odds ratio of 1.25 when the exposure variable of interest has a 30% prevalence and the test is being performed at the 5% alpha level. Now let us consider a statistical interaction test of an exposure between two groups. The test would be designed to determine if the ratio of the two odds ratios in the two groups were different or the same. Specifically, the interaction test is a test of whether the ratio of these two odds ratios is one. To be able to detect a ratio of the two odds ratios that is 1.25 or larger with 80% power with an exposure variable with a 30% prevalence and testing at the 5% alpha level would require twice the number of case control pairs or 1,440 cases. With 720 cases, there is at least 80% power to detect a ratio of two odds ratios on the order of magnitude of 1.38. This is not substantially different from the operating characteristics of the main effect comparisons. Thus there will be adequate power to detect small interactions with the proposed sample size.

For continuous variables, there is little impact on the power of proposed analyses to detect meaningful differences between case and control means in each of the above subgroup sizes. With 180 cases in a subgroup, it will be possible to detect differences of 0.34 standard deviations with 90% power when testing at alpha 0.05 (two sided test).

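### Section 12.2.3 says subgroup size hardly affects power for continuous variables, but its own formula takes power for 0.34 SD from 90% at 180 pairs to 67% at 100 and 40% at 50

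*Protocol*

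**What the plan says.** Section 12.2.3 announces power analyses "in subgroups representing 7%, 14%, 25%, 50% and 75% of the entire case control study population". Tables 3 to 12 carry these shares as 540, 360, 180, 100 and 50 case-control pairs. For binary exposures the section acknowledges that the detectable odds ratio depends strongly on the number of cases. It gives an example in which power falls from 95.0% to 83.7% to 54.8% at 540, 360 and 180 pairs.

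For continuous variables it says the opposite: "there is little impact on the power of proposed analyses to detect meaningful differences between case and control means in each of the above", meaning the sizes just listed. One figure follows in support: "With 180 cases in a subgroup, it will be possible to detect differences of 0.34 standard deviations". It is given for 90% power and a two-sided alpha of 0.05. No figure is given for 100 or 50 pairs.

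**The concern.** The statement covers every listed subgroup size, including the two smallest, yet the single supporting figure is for the middle one. The formula in Section 12.2.2 makes the detectable difference proportional to the square root of 1/N. Continuous variables therefore cannot escape the loss of sensitivity that the section describes for binary ones.

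Interpretation is what is at stake. Section 12.3.2.2 plans paired t-tests for continuous variables. Section 12.3.3 gives the substudies no power plan of their own and says that changes in sample size were dealt with in Section 12.2. Section 12.2.3 assigns the 7% and 14% sizes to small substudies. A reader relying on the statement would take a null difference in means from 50 or 100 pairs as informative when the comparison had limited power.

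**Working it through.** **Inputs**
- Total size: 720 pairs, one control per case (Sections 12.2.2 and 6.3.1).
- Subgroup sizes: 7%, 14%, 25%, 50% and 75% of 720 are 50.4, 100.8, 180, 360 and 540. Tables 3 to 12 use 50, 100, 180, 360 and 540.
- Test: two-sided alpha 0.05, so Zα = 1.960. For 90% power, Zβ = 1.2816, and the sum is 3.2415.
- Effect quoted for subgroups: 0.34 SD (Section 12.2.3).

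**Formulas.** With one control per case, the simplified formula of Section 12.2.2 is N = 2(Zα + Zβ)²σ²/(μ1 − μ0)². Rearranged:
- detectable difference at 90% power, in SD units: 3.2415 × √(2/N)
- power for a difference of d SD: Φ(d × √(N/2) − 1.960)

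**Reproducing the protocol's figure.** At N = 180 the detectable difference is 3.2415 × √(2/180) = 0.342 SD. Power for 0.34 SD is Φ(0.34 × 9.487 − 1.960) = Φ(1.266) = 89.7%. This agrees with the stated 90%, so the formula and the two-sided test are evidently those used.

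**Same formula at the other sizes**

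| Pairs | Share of 720 | Power for 0.34 SD | Detectable at 90% power |
|---|---|---|---|
| 720 | 100% | >99.9% | 0.17 SD |
| 540 | 75% | >99.9% | 0.20 SD |
| 360 | 50% | 99.5% | 0.24 SD |
| 180 | 25% | 89.7% | 0.34 SD |
| 100 | 14% | 67.2% | 0.46 SD |
| 50 | 7% | 39.7% | 0.65 SD |

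At 100 pairs: Φ(0.34 × 7.071 − 1.960) = Φ(0.444) = 67.2%. At 50 pairs: Φ(0.34 × 5 − 1.960) = Φ(−0.260) = 39.7%.

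From 540 to 50 pairs the detectable difference grows by √(540/50) = 3.3. Even the supporting figure of 0.34 SD is √(720/180) = 2 times the full-sample value.

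**Variants for 0.34 SD at 100 and 50 pairs**
- t-based power: 66–67% and 38–39%.
- Unsimplified formula with equal SDs: 66% and 39%.
- One-sided test: 78% and 52%.
- Paired analysis with correlation ρ, power Φ(d × √(N/(2(1 − ρ))) − 1.960). The protocol gives no ρ for continuous variables, so these values are assumptions: ρ = 0.25 gives 79.3% and 50.1%; ρ = 0.5 gives 92.5% and 67.2%.

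A constant ρ multiplies every detectable difference by the same √(1 − ρ), so the 3.3-fold change between 540 and 50 pairs is unaffected.

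**A separate point.** Section 12.2.2 states better than 90% power for 0.16 SD at 720 pairs. The two-sided formula gives Φ(0.16 × √360 − 1.960) = 85.9%. The table above uses the formula's own 0.17 SD, and nothing here depends on the 0.16 figure.

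**The case against.** The strongest defence is that the statement concerns meaningful differences, a term the protocol leaves undefined, and that the 0.34 SD sentence is limited to 180 cases and is correct there. The protocol never claims 0.34 SD at 50 or 100 pairs. Section 1.5.1 says large effects are hypothesised in certain substudies. If meaningful meant about 0.70 SD, power at 50 pairs would be Φ(0.70 × 5 − 1.960) = Φ(1.54), about 94%. The defence has further support:
- The same section warns in general terms that an effect detectable in one subgroup may be missed in another.
- At 540, 360 and 180 pairs, power for 0.34 SD (>99.9%, 99.5%, 89.7%) does hold up better than in the binary example.
- Pairing could help. With an assumed correlation of 0.5 the 14% subgroup reaches 92.5%.
- The subgroup comparisons are optional, and the study presents itself as hypothesis-generating. The two laboratory studies of 100 pairs (Sections 3.6.3 and 3.6.4) look at detection or culture positivity, to which the binary tables apply.

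Some of this stands. The 180-pair figure is right, the contrast with the binary example is fair at the three larger sizes, and the 14% result depends on a correlation the protocol does not give. The rest does not save the statement. The 0.70 SD effect (Sections 12.2.4 and 12.4) and the three-quarters of an SD (Section 1.5.2) belong to the clinical course study. The case-control power sections quote only 0.16 and 0.34 SD for continuous variables. A correlation of 0.5 still leaves 67% at 50 pairs, against 99.5% at 180. The general warning contradicts the statement and does not qualify it.

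**Conclusion.** The concern holds. By the protocol's own formula, power for the only effect size quoted for continuous variables in subgroups falls from 89.7% at 180 pairs to 67.2% at 100 and 39.7% at 50. The detectable difference at 90% power rises from 0.20 to 0.65 SD over the listed sizes. The section therefore claims a power property that the design does not have.

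The percentages rest on a two-sided 0.05 test, equal SDs and no within-pair correlation, as in Section 12.2.2. A positive correlation would raise power at every size without removing the dependence on subgroup size. The error affects how subgroup and substudy results would be read. It does not touch the main case-control comparison, so the change should be made but is not critical.

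**What to change.** In Section 12.2.3, delete the statement that subgroup size has little effect on power for continuous variables. Replace it with the difference detectable at 90% power, two-sided alpha 0.05, for each planned size:

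- 540 pairs (75%): 0.20 SD
- 360 pairs (50%): 0.24 SD
- 180 pairs (25%): 0.34 SD
- 100 pairs (14%): 0.46 SD
- 50 pairs (7%): 0.65 SD

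Add that in the 7% and 14% subgroups only moderate to large differences in means can be detected reliably. If credit is to be taken for pairing, state the assumed correlation and give the figures with and without it.

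The cost is one sentence and a five-line table. Sample size, design and conduct are unchanged.

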12.2.4 Statistical Power Considerations for the Clinical Course Study

For the clinical course study, investigators may assess if certain physiological measurements, such as the Forced Expiratory Volume in one second (FEV₁) are different among the five groups defined by sarcoidosis category. Other variables (such as indices of disease severity) may also be measured longitudinally for these groups. For simplicity, it will be assumed that the FEV₁ level is being analyzed. Measurements of FEV₁ will be made at baseline and two years. For the purpose of estimating the minimum power achievable in this study it will be assumed that each patient will provide one observation of FEV₁ after study entry. The study population will consist of a total of 240 cases; 48 in each of the five sarcoidosis subgroups.

The power evaluations for analysis of FEV_1 are based on a test for differences among normally distributed observations. The assumption of constant variance of the outcome variable within sarcoidosis subgroup is important for this test to be valid. If it is determined that this assumption is not true, a data transformation (such as a logarithmic transformation) will be used before the analysis proceeds.

There are ten possible pairwise comparisons that might be performed in the analyses of FEV₁. Let R₁, R₂, R₃, R₄ and R₅ be the means of FEV₁ levels in the five sarcoidosis groups. The alpha level for the six pairwise comparisons will be controlled at 0.05 by performing an F test of H₀:E(R₁)=E(R₂)=E(R₃)=E(R₄)=E(R₅), versus the alternative that the expected value of at least one of the means is different. The significance of the F test will be assessed at the 0.05 alpha level. The ten pairwise comparisons will be made only if the global F test is significant. In this case, each comparison will be made at the 0.05/6, (6 = the combinations of 4 things taken 2 at a time), comparison-wise alpha level. Hayter (Hayter, 1986) has shown that this procedure will control the family-wise error rate as well as the experiment-wise error rate.

The within-individual correlation is important for power calculations in a longitudinal data analysis. This power is minimized when the within-individual correlation is one or if only one measurement is taken per person. If the within-individual correlation is one, taking two measurements is not different from taking one measurement per patient. If the within-individual correlation decreases to zero, the repeated measures analysis increases the power to detect specified alternatives. It is advantageous to determine the worst case scenario (within-individual correlation =1) when making power assessments. Power will likely be higher than this worst case scenario.

Scheffé (Scheffé, 1959) has shown that the non-centrality parameter for the numerator chisquare is minimized when the expected values for the means in two of the above groups differ by Ä and the expected value for each of the remaining groups are exactly halfway between the other two expected values. In this case the noncentrality parameter for the numerator chi-square is dependent only on the value of Ä and ó (the within-group standard deviation of the end point). Specifically, one can use the following equation to calculate power curves for the proposed design:

$$\ddot{o}$$
 (1& \hat{a}) ' $\left[\frac{J}{2xI}\right]^{1/2}$ Ä/ó

where \ddot{o} (1- \hat{a}) is derived from the Pearson-Hartley tables (Scheffé, 1959) for V₁ = 4 and V₂ = 235 degrees of freedom; J is the number of individuals in each group (48); Éis the number of groups (I=5); and \dot{o} is the within-group standard deviation of the FEV₁ measurements.

Table 13 shows the power to detect specified differences Å (in terms of standard deviation units, Å/ó) with 70%, 80% and 90% power when testing at the 0.05 á level with 48 cases in each of the sarcoidosis categories. The proposed study size of 240 cases (48 in each sarcoidosis group) is sufficient (power \geq 80%) to detect a difference in the two true FEV₁ means of 0.70 standard deviations or more.

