1.5.2 Clinical Course Study

The clinical course study is conducted on the first 240 cases enrolled into ACCESS; each Clinical Center is expected to contribute at least 20 cases. The total number of cases is sufficient to detect small changes in means (three-quarters of a standard deviation) among defined subgroups, and moderate changes (odds ratios of 3) in categorical outcomes.

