Initially cases are recruited at each participating Clinical Center sequentially without regard to the proportion in each category. If cases are identified from more than one patient source (e.g., different clinics or practices) within the Clinical Center, efforts are made to enroll every patient from each patient source over the period of the study year. Clinical Coordinating Center staff review the distribution of enrolled cases periodically to ensure that appropriate proportions of cases in each category are enrolled by the end of the recruitment period. Assessment occurs after each 150 incident cases have been enrolled in the study. Based on each analysis, Clinical Centers may be required to adjust the proportion of cases recruited for each category.

Clinical Center Coordinators complete screening logs for data entry and submission to the Clinical Coordinating Center. Cases are considered potential participants if their records show they

6-4
satisfy sarcoidosis eligibility criteria. Those deemed eligible are invited to participate in the study. For those cases who are ineligible for further consideration in ACCESS no questionnaire data will be collected. Data collected on those who are ineligible or refuse to participate in the study include basic demographics (age, race, gender), type of health care coverage (private insurance, managed care, no insurance, Medicare, Medicaid), and reasons for ineligibility or refusal to participate. Completion of screening logs for cases was discontinued in October 1997.

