8.3 CLINICAL COURSE STUDY

The process of recruitment for the follow-up study begins with the first case enrolled in the etiology study and continued until the end of September 1997 when 243 cases were enrolled in the Clinical Course Study. For cases agreeing to participate, a clinic visit is scheduled approximately 24 months after the patient's baseline evaluation. Cases enrolled after June 1997 may be seen in the interval 21 to 24 months after entry. The follow-up evaluation includes a medical history, physical examination, chest X-ray, spirometry, routine biochemistry, complete blood count and differential, and additional tests as clinically indicated. A follow-up blood specimen is collected. Clinical Center staff contact these ACCESS cases by telephone at 6, 12 and 18 months after entry. The telephone call is designed to maintain contact with the patient and to ask about the patient's general well being. A timeline for the Clinical Course study data collection is presented in Figure 8-1.

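### The Clinical Course power figure assumes 48 cases in each of five categories, but the design does not produce equal categories, so pairs of small categories may have less power than stated

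*Protocol*

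**What the plan says.** Protocol section 12.2.4 plans a comparison of mean FEV₁ across five sarcoidosis categories: "The study population will consist of a total of 240 cases; 48 in each of the five sarcoidosis subgroups". The global test comes first: "The significance of the F test will be assessed at the 0.05 alpha level". Table 13 gives detectable differences of 0.62, 0.70 and 0.80 SD at 70%, 80% and 90% power, and section 12.4 repeats 0.70 SD in its conclusions.

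The section describes its result as a lower bound, in a particular sense: "For the purpose of estimating the minimum power achievable in this study it will be assumed that each patient will provide one observation of FEV₁". It adds: "It is advantageous to determine the worst case scenario (within-individual correlation =1) when making power assessments".

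On how the cohort is formed, section 1.5.2 takes the first 240 cases, with at least 20 expected from each Clinical Center, and section 9.3 makes every case enrolled in the interval eligible. Section 6.2 says: "Initially cases are recruited at each participating Clinical Center sequentially without regard to the proportion in each category". The same section has the category mix assessed after each 150 cases and allows centers to be told to change it. No target proportions are given. Section 8.3 records that this recruitment ended in September 1997, "when 243 cases were enrolled in the Clinical Course Study".

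**The concern.** The calculation treats 48 per category as a fact about the cohort, yet no rule sets category sizes; the only quota is by center. The protocol's own background suggests uneven categories. Section 2.1 puts lung involvement at 90%, eye and skin involvement at about 25%, and symptomatic involvement of other organs below 10%.

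Section 3.1 makes the relation between initial category and category at 24-30 months an objective, and section 9.8 expects subgroup-specific risk factors for progression. If a rare category shows no difference, a reader will judge that result against a claimed 80% power that the comparison may not have had.

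**Working it through.** **Inputs from section 12.2.4.** Five groups (I = 5), J = 48 per group, alpha 0.05, degrees of freedom 4 and 235. Two means differ by Δ and the other three lie halfway between. All 240 cases are taken to have a two-year value, as in the protocol.

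**Reproducing the stated figure.** The protocol's φ = √(J/(2I)) · Δ/σ corresponds to a non-centrality λ = I·φ² = J(Δ/σ)²/2. The critical F(4, 235) at 0.05 is 2.41.

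- Δ/σ = 0.70: λ = 48 × 0.49 / 2 = 11.76, φ = 1.53, power 78.4% (stated 80%).
- Δ/σ = 0.80: λ = 15.36, φ = 1.75, power 89.2% (stated 90%).
- Δ/σ = 0.62: λ = 9.23, φ = 1.36, power 66.6% (stated 70%).

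The 0.70 and 0.80 entries agree to within two points. The 0.62 entry is 3.4 points high; 70% power needs 0.64 SD. With equal groups, 80% power needs 0.71 SD. The arithmetic is therefore broadly sound, and the issue is the input of 48.

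**Unequal groups.** For a pair with sizes n₁ and n₂ that differ by Δ, the smallest λ is h(Δ/σ)², where h = n₁n₂/(n₁+n₂). It occurs when the other means sit at the pair's weighted mean. With other means at the plain midpoint, λ = ¼[(n₁+n₂) − (n₁−n₂)²/240](Δ/σ)², which is equal or slightly larger.

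**Why equal groups are the ceiling for the weakest pair.** The two smallest of five groups hold at most 2/5 of 240 = 96 cases. So h ≤ 48 × 48 / 96 = 24, and equality needs 48 in each group. The midpoint formula has the same bound, ¼ × 96 = 24. This result does not depend on any assumed split.

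**Illustrations.** The protocol gives no category counts, so these splits of 240 are assumptions. Power is at 0.70 SD under the smallest λ, with the midpoint value in brackets where it differs for the smallest pair.

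| Split | Smallest pair, h | Power, smallest pair | SD for 80% power, smallest pair | Power, largest pair |
|---|---|---|---|---|
| 48 × 5 | 24.0 | 78% | 0.71 | 78% |
| 72/60/48/36/24 | 14.4 | 53% (55%) | 0.92 (0.91) | 91% |
| 96/60/36/24/24 | 12.0 | 45% | 1.01 | 94% |
| 120/48/36/24/12 | 8.0 | 31% (34%) | 1.23 (1.17) | 92% |
| 144/48/24/12/12 | 6.0 | 24% | 1.43 | 93% |

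For the second row, h = 36 × 24 / 60 = 14.4 and λ = 14.4 × 0.49 = 7.06.

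**With the section 6.2 adjustment used in full.** Suppose the first 150 cases fall 50/20/15/10/5% and all of the remaining 90 go to the small categories. The result is 75 and four groups of 41.25, so h = 20.6 and power is 71%. Starting from 60/20/10/5/5%, it is 90 and four groups of 37.5, so h = 18.75 and power is 66%.

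**The case against.** Several stronger readings are tempting, and the documents do not support them.

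- **That the section mislabels its result as a minimum.** It does not do so on its own terms. The sentence continues to one FEV₁ observation per patient, and the worst case is defined as a within-individual correlation of one. In that sense the word is valid. It simply does not extend to category size, which the section never varies.
- **That the stated figure is really the best case.** This is true only for the lowest-power pair. Pairs of large categories gain power (91-94% in the table), and section 12.2.4 itself notes that repeated measures could raise power.
- **That category is ignored throughout recruitment.** Section 6.2 says initially, and it permits adjustment after 150 cases, which could act on the last 90 of the 240. But adjustment is optional. It aims at unspecified proportions by the end of all recruitment, not at equal groups in this cohort. Even full use leaves the weakest pair below the stated power in the two starts examined.
- **That the size of the loss is known.** It is not, because every split above is assumed. Only the direction is certain.
- **That the section 1.5.2 claim about "moderate changes (odds ratios of 3) in categorical outcomes" fails because two groups of 48 cannot support it.** Section 1.5.2 ties that claim to the total number of cases, not to two categories of 48. For 120 against 120, power at an odds ratio of 3 is 79-99% over reference rates of 10-80%. At most, one could ask for the split and outcome rate to be stated.

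It is also fair to say that the analysis is framed as something investigators may do, and that section 12.4 calls the power work preliminary. That limits the weight of the point but does not make the input correct.

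**Conclusion.** The point holds in a limited form. The claim of at least 80% power at 0.70 SD depends on equal categories that the design does not produce. Equal allocation is the ceiling for the weakest pair at a total of 240, so any imbalance puts pairs of small categories below the stated power and pairs of large categories above it. In the assumed splits the smallest pair has about 24-55% power, or about 66-71% if the last 90 cases were fully steered. These figures take two-year values for all 240 cases and rest on category counts that the protocol does not report. The calculation should be restated; the cohort and the test need not change.

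**What to change.** In section 12.2.4, replace 48 per group with the actual category counts of the 243 enrolled cases. Use the hierarchical classification of Table 6-2A, whose groups are mutually exclusive. Table 6-2B counts each involvement independently, so its groups can overlap. State the difference detectable with 80% power for the smallest and for the largest pair of categories, and carry both into Table 13 and section 12.4. Add a sentence saying that the minimum refers only to one observation per patient and not to category size. Section 1.5.2 needs no correction on this account; if it is touched, state the split and outcome rate for which an odds ratio of 3 is detectable.

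The cost is a recalculation for cases already enrolled and categorised, with no new patients or data. The downside is that the figure for small categories will look less favourable.

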	0.3	0.063	0.101	0.159	0.271	0.610	0.768	0.796	0.572
	0.5	0.047	0.066	0.093	0.142	0.300	0.385	0.375	0.214
	0.6	0.041	0.054	0.071	0.101	0.193	0.239	0.226	0.131
	0.7	0.036	0.044	0.054	0.072	0.119	0.141	0.131	0.082
	0.8	0.032	0.036	0.042	0.050	0.072	0.080	0.075	0.054
	0.9	0.028	0.030	0.032	0.036	0.043	0.045	0.043	0.036
	1.0	0.025	0.025	0.025	0.025	0.025	0.025	0.025	0.025
	1.1	0.028	0.030	0.032	0.035	0.041	0.043	0.041	0.034
	1.2	0.031	0.035	0.040	0.047	0.062	0.066	0.060	0.045
	1.3	0.034	0.041	0.049	0.061	0.089	0.095	0.084	0.056
	1.4	0.038	0.047	0.059	0.077	0.121	0.130	0.111	0.068
	1.5	0.041	0.053	0.070	0.096	0.158	0.169	0.140	0.080
	1.6	0.045	0.060	0.082	0.116	0.198	0.210	0.172	0.093
	1.7	0.048	0.068	0.094	0.139	0.240	0.253	0.204	0.105
	1.8	0.052	0.075	0.108	0.163	0.285	0.298	0.236	0.118
	1.9	0.056	0.083	0.122	0.188	0.330	0.342	0.268	0.130
	2.0	0.060	0.092	0.137	0.214	0.375	0.385	0.300	0.142
	3.0	0.103	0.189	0.312	0.491	0.726	0.705	0.552	0.244
	4.0	0.152	0.298	0.487	0.704	0.884	0.851	0.695	0.315
	5.0	0.202	0.405	0.632	0.833	0.946	0.915	0.775	0.365
	10	0.448	0.772	0.935	0.987	0.995	0.983	0.902	0.479
	15	0.635	0.914	0.985	0.998	0.999	0.992	0.932	0.521
	20	0.762	0.965	0.996	0.999	0.999	0.995	0.944	0.543

Table 13

Maximum Effect Size That Can Be Detected With Specific Power Analysis of Variance (One Comparison $\acute{a} = 0.05$) (N = 240)

Power	70%	80%	90%
Ä/ó	0.62	0.70	0.80

CHAPTER 13

TRAINING AND CERTIFICATION PROCEDURES

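### The 80% power stated for a 0.70 SD difference between two category means is global F-test power; under the plan's own two-step rule it is about 74%

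*Protocol*

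**What the plan says.** Section 12.2.4 takes FEV₁ as its worked example and assumes equal groups: "The study population will consist of a total of 240 cases; 48 in each of the five sarcoidosis subgroups". It sets a two-step rule. First comes a global test: "The significance of the F test will be assessed at the 0.05 alpha level". Then: "The ten pairwise comparisons will be made only if the global F test is significant", each at 0.05/6, where 6 is explained as the number of pairs among four things.

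The power derivation uses the F test alone, on 4 and 235 degrees of freedom. The means are in the least favourable arrangement: two groups differ by Δ and the other three sit midway. Table 13 is introduced as giving differences detectable with "70%, 80% and 90% power when testing at the 0.05 á level with 48 cases in each of the sarcoidosis categories". Its entries are 0.62, 0.70 and 0.80 SD, and its title begins "Maximum Effect Size That Can Be Detected With Specific Power".

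The text then concludes "The proposed study size of 240 cases (48 in each sarcoidosis group) is sufficient", at power of 80% or more, "to detect a difference in the two true FEV₁ means of 0.70 standard deviations or more". Section 12.4 repeats 0.70 SD as adequately powered at the 0.05 level for comparing the five groups. Section 1.5.2 gives a looser figure for the same sub-study: "small changes in means (three-quarters of a standard deviation) among defined subgroups".

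**The concern.** The sentence is worded as power to detect a difference between two means. Under the plan's rule that takes two successes, a significant F test and a significant pairwise test at the reduced level. The second step does not enter the calculation. A reader planning or interpreting category comparisons would take 0.70 SD as the pairwise difference the cohort can show with 80% power, when that figure belongs, approximately, to rejecting equality of all five means. The two overview statements, 0.70 SD in 12.4 and 0.75 SD in 1.5.2, also need to rest on one stated procedure.

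**Working it through.** **Inputs, all from 12.2.4.** I = 5 groups, J = 48 per group, F test at α = 0.05 with 4 and 235 df, pairwise tests at 0.05/6 = 0.00833 (taken as two-sided, since the section does not say), means at −Δ/2, 0, 0, 0, +Δ/2, and one post-entry observation for every patient.

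**Step 1: the plan's own figure (global F test).**
φ = √(J/(2I)) × Δ/σ = √(48/10) × 0.70 = 1.534.
λ = J(Δ/σ)²/2 = 48 × 0.49/2 = 11.76.
The non-central F on 4 and 235 df gives 78.4%, close to the stated 80% but below it.

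| Table 13 entry (SD) | Stated power | Exact F-test power | Exact SD for stated power |
|---|---|---|---|
| 0.62 | 70% | 66.6% | 0.64 |
| 0.70 | 80% | 78.4% | 0.71 |
| 0.80 | 90% | 89.2% | 0.81 |

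**Step 2: the pairwise test alone.**
Non-centrality = 0.70 × √(48/2) = 3.43. The non-central t on 235 df at 0.05/6 gives 77.8% (normal approximation 78.6%). Also requiring a significant F can only lower this, so 77.8% is a ceiling for a given pair.

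**Step 3: both steps.** Simulation, 1,000,000 replicates, variance pooled on 235 df:

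| Difference (SD) | F and pair at 0.05/6 | F and pair at 0.05/10 |
|---|---|---|
| 0.62 | 60.0% | 56.3% |
| 0.70 | 73.9% | 70.9% |
| 0.74 | 79.7% | 77.0% |
| 0.75 | 81.0% | 78.6% |
| 0.76 | 82.3% | 79.9% |
| 0.80 | 86.9% | 84.9% |

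So 80% power needs about 0.74 SD with divisor 6 and about 0.76 SD with divisor 10.

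**Step 4: other placements of the three remaining means**, 0.70 SD, 0.05/6. Evenly spaced means give 76.4%. One mean apart from the other four gives 77.5%. A three-against-two split gives 77.9%, which equals the 77.8% ceiling within simulation error. None reaches 80% for the given pair.

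**Step 5: the divisor.** Five groups give 5 × 4/2 = 10 pairs; four give 4 × 3/2 = 6. Section 12.2.4 names ten comparisons yet divides by 6.

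**The case against.** The best defence is that the basis is disclosed. The derivation is openly a non-central F calculation, Table 13 is labelled as an analysis of variance at 0.05, and 12.4 speaks of comparing five groups. The two means in the disputed sentence can be read as the two that define Δ in the least favourable configuration. On that reading 78.4% is near 80%, and the complaint is mainly about wording. That largely stands as an account of how the figure arose. It does not make the sentence right: 78.4% is still not 80% or more, and the section's own rule for declaring a pair different is stricter.

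The Table 13 shifts are small. The section says its values come from printed tables, and the large-sample limit gives 79.3% at 0.70 SD and 89.9% at 0.80 SD. Only the 70% entry is more than 2 points out, and no claim in the text relies on it.

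Three stronger readings are tempting but unsupported:
- That 0.75 SD should simply replace 0.70 SD. This holds with divisor 6 (81.0%) but not with divisor 10 (78.6%).
- That power is really 60 to 68% once missed visits are counted. Those values need an assumed 10 to 20% loss. Section 12.3.6 expects some missing data but gives no rate.
- That no pairwise finding could reach 80%. The ceiling applies to a given pair. If any significant pair counts, power is 77.3% in the plan's configuration but higher in some others (85.4% with evenly spaced means).

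**Conclusion.** The power statement is wrong as written, by a modest amount. At 0.70 SD with 48 per group, exact power is 78.4% for the global F test and about 74% for the two-step rule in the plan's own configuration, with a ceiling of 77.8% for a given pair. Neither reading gives 80%. The pairwise difference detectable with 80% power is about 0.74 SD at 0.05/6 or about 0.76 SD at 0.05/10.

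These results assume equal groups, a common variance, two-sided pairwise tests and one observation from every patient. A reader might infer that the clinical course study is too small. The documents do not support that: the shift is a few hundredths of an SD, FEV₁ is an illustrative outcome in the secondary cohort, and 12.2.4 presents the single-observation case as a worst case relative to the repeated-measures analysis.

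**What to change.** 1. In 12.2.4, reconcile the divisor with the number of comparisons before restating any figure.
2. In 12.2.4 and 12.4, give the pairwise difference detectable with 80% power under the two-step rule: about 0.74 SD if 0.05/6 is kept, about 0.76 SD if 0.05/10 is adopted. If the F-test figure is also kept, label it as such.
3. Check the 0.75 SD in 1.5.2 against that choice: power is 81.0% with divisor 6 and 78.6% with divisor 10.
4. Retitle Table 13 as the minimum detectable difference for the global F test, with 0.64, 0.71 and 0.81 SD for 70, 80 and 90% power.
5. State that these figures assume no missed 24-month visits. Any figure after loss should be marked as resting on an assumed rate.

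The cost is edited text and numbers. Sample size and data collection do not change; adopting 0.05/10 would also change the pairwise significance threshold.
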